7.5.3 Local Tolerability Assessments

Subject and Investigator assessments will be included in separate tables and listings, with the count and percentage of subjects within each severity (maximum severity assessed at either axilla) and treatment group presented by parameter and visit.

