This was a Phase 1, randomized, double-blind, single-center study conducted in 24 subjects with primary axillary hyperhidrosis. The objective of this study was to investigate the local tolerability, safety, and effect of BBI-4000 DB20 gel on sweat production (using gravimetric and Hyperhidrosis Disease Severity Scale [HDSS] methods). The study consisted of 2 consecutive cohorts, where Cohort 1 (N = 6) established acceptable tolerability of 5% BBI-4000 DB20 gel (applied to one axilla) and vehicle gel to the other axilla prior to enrolling a separate group of subjects into Cohort 2. Subjects in Cohort 2 (N = 18; 6 in each group) were randomized to receive 5% BBI-4000 DB20 gel, 10% BBI-4000 DB20 gel, or vehicle gel (control) to both axillae once daily for 14 days.

All 24 subjects completed the study. Local tolerability assessments indicated that 5% and 10% BBI-4000 DB20 gel topically applied to the axilla region was well tolerated over the 14-day treatment period. Minimal to mild erythema, itching, burning, and dryness were reported during treatment, usually limited to only 1 study visit and resolved spontaneously. No AEs, SAEs or deaths were reported.

The primary endpoint of mean percent reduction from baseline in sweat production at Day 15 was 63.2% and 67.6% for subjects treated with 5% and 10% BBI-4000 DB20 gel, respectively (compared to 52.4% subjects treated with vehicle gel). Overall, the subjects receiving BBI-4000 experienced better efficacy outcomes. Specifically, 67% of subjects receiving BBI-4000 DB20 gel (5% and 10% groups combined) achieved a \geq 2-point improvement in the HDSS in comparison to 33% of subjects who received vehicle; and 75% of subjects receiving BBI-4000 (5% and 10% groups combined) achieved \geq 50% sweat reduction compared to 33% of subjects who received vehicle. While BBI-4000 10% appeared to have a greater effect than BBI-4000 5% DB20 gel with regard to several efficacy outcomes, a larger study was required to confirm this potential difference.

Study BBI-4000-CL-201

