10.4 Safety Analyses

Safety variables are AEs, blood laboratory evaluations, UPTs (as required), local tolerability assessments and vital signs.

Adverse events will be coded from the verbatim text into preferred term (PT) and primary system organ class (SOC) using the most current version of Medical Dictionary for Regulatory Activities (MedDRA). Treatment-emergent AEs will be summarized in the following tables: all reported AEs, all treatment-related AEs, all SAEs, and AEs leading to investigational product discontinuation. The number and percent of subjects reporting the AE at least once will be tabulated according to the highest severity reported.

Laboratory evaluations and UPTs parameters will be summarized.

Vital signs, including changes from baseline, will be summarized by descriptive statistical methods as previously described.

Local tolerability assessments will also be summarized similarly as the treatment related AEs.

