- Subject incidence of SAEs by MedDRA system organ class and preferred term
- Subject incidence of SAEs related to study drug by MedDRA preferred term.

At each level of summarization (e.g., any AE, system organ class, and preferred term), subjects experiencing more than one TEAE will be counted only once. In the summaries of TEAEs by severity grade, subjects will be counted once at the highest severity reported at each level of summarization, and by each level of severity; in the summary of TEAEs by relationship, subjects will be counted once at the closest relationship to study drug.

Adverse event data will be presented in data listings by subject, treatment group, and event. Serious AEs and AEs leading to discontinuation of the study drug will be presented in separate data listings.

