Note: Subjects reporting more than one related adverse event are counted only once. Summary includes all related events (i.e., “Possibly Related,” “Probably Related,” or “Definitely Related” to study drug).

^[1] Adverse events are coded to preferred term using the Medical Dictionary for Regulatory Activities (MedDRA), version 19.1.

Reference: *Listing #(s)*
Path\filename.sas ddmmmyyy hh:mm

Programming Note: Sort events by descending order of preferred term incidence, based on the overall incidence (i.e., sum over all treatment groups)

Table 14.3.1.9
Local Tolerability Assessments – Subject Assessments
Safety Population

Parameter	Visit	Vehicle (N=) Baseline Assessment ^[1]						BBI-4000 5% (N=) Baseline Assessment ^[1]					
		Absent	Minimal	Mild	Moderate	Severe	Missing	Absent	Minimal	Mild	Moderate	Severe	Missing
Itching	Day 8	(n=)						(n=)					
	Absent	n (x.x%)	n (x.x%)	n (x.x%)	n (x.x%)	n (x.x%)	n (x.x%)	n (x.x%)	n (x.x%)	n (x.x%)	n (x.x%)	n (x.x%)	n (x.x%)
	Mild	n (x.x%)	n (x.x%)	n (x.x%)	n (x.x%)	n (x.x%)	n (x.x%)	n (x.x%)	n (x.x%)	n (x.x%)	n (x.x%)	n (x.x%)	n (x.x%)
	Moderate	n (x.x%)	n (x.x%)	n (x.x%)	n (x.x%)	n (x.x%)	n (x.x%)	n (x.x%)	n (x.x%)	n (x.x%)	n (x.x%)	n (x.x%)	n (x.x%)
	Severe	n (x.x%)	n (x.x%)	n (x.x%)	n (x.x%)	n (x.x%)	n (x.x%)	n (x.x%)	n (x.x%)	n (x.x%)	n (x.x%)	n (x.x%)	n (x.x%)
	Missing	n (x.x%)	n (x.x%)	n (x.x%)	n (x.x%)	n (x.x%)	n (x.x%)	n (x.x%)	n (x.x%)	n (x.x%)	n (x.x%)	n (x.x%)	n (x.x%)
...													

Abbreviation: ET, early termination

Notes:

- Tolerability is assessed on a 5-point scale where 0= Absent, 1= Minimal, 2= Mild, 3= Moderate, 4= Severe.
- Subjects self-evaluate Itching and Burning for each axilla prior to the Investigator’s evaluation.
- Maximum severity assessed for either axilla is reported.

^[1] Baseline is defined as the last available measurement taken prior to the first dose of study drug.

Reference: Listing #(s)

Path\filename.sas ddmmmyyyy hh:mm

Programming Note: Continue for Days 15, 22, 29, 36, 43, and 57, parameter Burning, for all BBI-4000 doses (10%, 15%).

Table 14.3.1.10
Local Tolerability Assessments – Investigator Assessments
Safety Population

Parameter	Visit	Vehicle (N=)					BBI-4000 5% (N=)				
		Baseline Assessment ^[1]					Baseline Assessment ^[1]				
		Absent	Mild	Moderate	Severe	Missing	Absent	Mild	Moderate	Severe	Missing
Dryness	Day 8	(n=)					(n=)				
	Absent	n (x.x%)	n (x.x%)	n (x.x%)	n (x.x%)	n (x.x%)	n (x.x%)	n (x.x%)	n (x.x%)	n (x.x%)	n (x.x%)

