	Mild	n (x.x%)	n (x.x%)	n (x.x%)	n (x.x%)	n (x.x%)	n (x.x%)	n (x.x%)	n (x.x%)	n (x.x%)	n (x.x%)
	Moderate	n (x.x%)	n (x.x%)	n (x.x%)	n (x.x%)	n (x.x%)	n (x.x%)	n (x.x%)	n (x.x%)	n (x.x%)	n (x.x%)
	Severe	n (x.x%)	n (x.x%)	n (x.x%)	n (x.x%)	n (x.x%)	n (x.x%)	n (x.x%)	n (x.x%)	n (x.x%)	n (x.x%)
	Missing	n (x.x%)	n (x.x%)	n (x.x%)	n (x.x%)	n (x.x%)	n (x.x%)	n (x.x%)	n (x.x%)	n (x.x%)	n (x.x%)
	...										

Abbreviation: ET, early termination

Notes:

- Tolerability is assessed on a 5-point scale where 0= Absent, 1= Minimal, 2= Mild, 3= Moderate, 5= Severe.
- Investigators evaluate Dryness, Scaling, and Erythema for each axilla after the Subject's evaluation.
- Maximum severity assessed at either axilla is reported.

^[1] Baseline is defined as the last available measurement taken prior to the first dose of study drug.

Reference: Listing #(s)

Path\filename.sas ddmmmyyy hh:mm

Programming Note: Continue for Days 15, 22, 29, 36, 43, and 57, parameters Scaling and Erythema, and BBI-4000 doses (10%, 15%)

Table 14.3.2.1
Listing of Deaths
Safety Population

Subject ID	Treatment Group	Date of Death (Study Day ^[1])	Cause of Death
xxx-xxxx	Vehicle / BBI-4000 5% / BBI-4000 10% / BBI-4000 15%	ddMMMyyyy (xx)	Adverse event or cause of death from the study exit form
xxx-xxxx			
...			

^[1] Time (days) relative to date of first dose of study drug

Path\filename.sas ddmmmyyyy hh:mm

Table 14.3.2.2
Listing of Serious Adverse Events
Safety Population

Subject ID	Treatment Group	System Organ Class ^[1] / Preferred Term ^[1] / Event Name	In the Treatment Area?	Start Date (Study Day ^[2])	End Date (Study Day ^[2])	Serious Criteria	Severity	Relationship to Study Drug	Action Taken with Study Treatment	Action Taken to Treat Event	Outcome

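### Local tolerability is tabulated only visit by visit, so the SAP will not report how many subjects ever had a reaction, which protocol 10.4 most naturally calls for

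*SAP*

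**What the plan says.** Protocol 10.4 gives the rule for local tolerability in one sentence: "Local tolerability assessments will also be summarized similarly as the treatment related AEs". The adverse event rule in the same section reads: "The number and percent of subjects reporting the AE at least once will be tabulated according to the highest severity reported".

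SAP 7.5.3 plans separate tables for subject and investigator assessments, with counts and percentages in each severity category, "maximum severity assessed at either axilla) and treatment group presented by parameter and visit". The layouts in Appendix B follow this. Table 14.3.1.9 (itching and burning) cross-tabulates baseline severity against Day 8 severity, then instructs: "Continue for Days 15, 22, 29, 36, 43, and 57, parameter Burning". Table 14.3.1.10 (dryness, scaling, erythema) has the same structure and notes: "Maximum severity assessed at either axilla is reported". Neither has a block for any visit or for the worst value over time. Appendix A lists no other tolerability table, only the by-subject Listings 16.2.7.2 and 16.2.7.3.

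For treatment-emergent adverse events by severity, SAP 7.5.2 keeps the per-subject rule: "subjects will be counted once at the highest severity reported at each level of summarization". For laboratory data, SAP 7.5.5 plans a shift to the worst post-baseline value. SAP section 4 promises to explain departures from the protocol's methods, and SAP 7.7 lists several, but none on tolerability.

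**The concern.** Local tolerability is part of a primary objective (protocol 3.1), across three strengths of a reformulated gel. The natural question is what share of subjects in each arm had burning, itching, dryness, scaling or erythema at any time on treatment, and how bad it got. A series of visit-specific tables does not answer it. The same visit percentages can come from a few subjects with a persistent reaction or from many subjects with one brief reaction each, and a reader comparing doses could not tell these apart from the summary tables.

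The brief pattern is the one the protocol leads us to expect. In the first axillary study the signs were "usually limited to only 1 study visit and resolved spontaneously", and the larger Phase 2 axillary study is also described as showing mostly transient signs. With the per-subject rule kept for adverse events and a worst-value rule for laboratory data, its absence here looks like an oversight.

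**Working it through.** The documents give no expected tolerability rate, so there is no stated figure to reproduce. The check compares the texts and then asks what by-visit counts can and cannot determine.

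**Texts side by side**

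- Unit of count: the protocol's adverse event rule counts a subject once if affected at least once. SAP 7.5.3 counts a subject afresh at each visit.
- Meaning of maximum: in protocol 10.4, the highest severity reported. In SAP 7.5.3 and both layouts, the worse of right and left axilla at one visit.
- Declaration: nothing in SAP 7.7.

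**Inputs for the illustration**

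- Post-baseline tolerability visits in the Time and Events Table: Visits 6, 7, 8, 9, 10, 13 and 14. The first six (Days 8, 15, 22, 29, 36, 43) cover treatment; Day 57 is follow-up. So V = 6.
- Subjects per arm: 220 / 4 = 55.
- Visit prevalence p: assumed at 5% and 10%, as neither document states one.

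**Range of ever-affected rates for a given visit prevalence**

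If prevalence is p at each of V visits, and all subjects attend, the share ever affected lies between p (same subjects each time) and V × p (no subject affected twice). If visits were independent it would be 1 − (1 − p)^V.

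- p = 5%: lower bound 5%; upper bound 6 × 5% = 30%; independence 1 − 0.95^6 = 26.5%. In an arm of 55 this is 0.05 × 55 = 2.75 to 0.30 × 55 = 16.5 subjects.
- p = 10%: lower bound 10%; upper bound 6 × 10% = 60%; independence 1 − 0.90^6 = 46.9%.

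**The same relation from the other side**

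If a share C is ever affected, each for d of the six visits, with onsets spread evenly, the average visit prevalence is C × d / 6. C is an assumption, shown over a range:

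- d = 1: C of 10%, 20%, 30%, 40% appears as 1.7%, 3.3%, 5.0%, 6.7% per visit.
- d = 2: the same C appears as 3.3%, 6.7%, 10.0%, 13.3%.
- d = 6: the two summaries agree.

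The understatement is therefore up to six-fold for one-visit reactions and nil for persistent ones. The summary tables do not say which case applies.

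**Subjects who stop after a reaction**

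Suppose 3 of 55 in an arm react at Day 8 and then leave. The Day 8 block shows 3/55 = 5.5%, the same as a per-subject count would give. Only later rows change: the number observed falls to 55 − 3 = 52, with the three in the Missing category unless an early-termination assessment is slotted into Day 43.

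**The case against.** The strongest reply is that the reactions that matter most are already counted per subject. Protocol 8.2.6 and SAP 6.4.2.2 require a tolerability sign to be recorded as an adverse event if it needs other therapy, interrupts dosing or ends participation. It then enters the tables that count each subject once at the highest severity. Table 14.3.1.1 has rows for discontinuation, interruption and events in the treatment area, and Table 14.3.2.3 lists each event that changed dosing. Early leavers are asked for the Visit 13 evaluations (protocol 7.4), and SAP 7.5 keeps all data up to termination. This stands. A reader might infer that subjects who leave for intolerance vanish from the results. The documents do not support that: these subjects thin out only in the later tolerability rows.

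A reader might also infer that such leaving is likelier on active gel and so makes later visits look better. That is not established for local signs. In the Phase 2 axillary study one of 189 subjects discontinued for an adverse event, and local signs were reported as broadly similar across groups. The three withdrawals described in the protocol's risk section were attributed to anticholinergic events, and only one of them included a local sign, application site dryness.

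Three further replies stand in part:

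- The protocol's tolerability sentence is loose. The per-subject rule is written for adverse events and reaches tolerability by the word similarly, so this is the natural reading, not an explicit commitment.
- No score is lost, because the listings hold every score by subject, axilla and visit. Listings are not a summary, however.
- A bare worst-severity table would count signs already present at baseline, so the remedy must use the baseline score.

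The adverse event tables still leave a gap. They use three severity grades against five for tolerability, and a score that prompted no action need not appear in them at all.

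**Conclusion.** The point holds as a reporting gap with an undeclared departure from the natural reading of protocol 10.4. The planned tables cannot give the number of subjects ever affected by each sign, or their worst severity. The gap concerns mainly transient scores that needed no action. Its possible size is up to a six-fold difference between visit prevalence and the share ever affected (5% per visit fits 5% to 30%). This assumes six on-treatment visits, full attendance and a constant visit prevalence. The upper end needs reactions confined to one visit. The earlier evidence points that way, but the one-visit description comes from a 14-day study of 24 subjects, so it may not carry over fully to 42 days.

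The point does not show that tolerability will be misreported in a particular direction between arms, and it does not touch the efficacy analyses. It should be corrected because the outcome is a primary objective and the correction is simple.

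**What to change.** Keep the by-visit tables. Add one table per assessor giving, for each sign and arm, the number and percent of Safety Population subjects by worst post-baseline severity in either axilla, over all scheduled, unscheduled and early-termination assessments. Cross-classify by baseline severity, or restrict to worsening from baseline, so that pre-existing signs are not counted as reactions. Use subjects with at least one post-baseline score as the denominator, and state it. Show on-treatment visits separately from Day 57 if wanted.

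State in SAP 7.5.3 how early-termination and unscheduled scores are assigned; both layouts define an early-termination abbreviation but show no row for it. Record the reconciliation with protocol 10.4 in SAP 7.7. While the layouts are open, correct the note to Table 14.3.1.10 that codes Severe as 5 on a 0 to 4 scale, and check that the Minimal category appears throughout both tables.

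The cost is two summary tables programmed from data already collected, plus short text edits to the SAP. No new assessments are needed.

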7.5.4 Deaths, Other Serious Adverse Events, and Other Significant Adverse Events

All deaths during the study, including the post-treatment follow-up period, will be listed by subject, to include the primary cause of death and investigator narratives. Serious AEs and other significant AEs, including those that led to withdrawal, interruption, or dose reduction of the study drug, will be provided in separate subject data listings.

7.5.5 Clinical Laboratory Evaluation

All descriptive summaries of laboratory results will be based on data analyzed by the central laboratory and presented in Système International (SI) units, as suggested by the Center for Biologics Evaluation and Research and the Center for Drug Evaluation and Research *Position on Use of SI Units for Lab Tests* (Oct 2013). All data will be included in by-subject data listings. Laboratory measurements identified as abnormal (i.e., outside the normal range) will also be listed separately by subject, laboratory test, and unit.

Clinical laboratory measurements, including serum chemistry and hematology, will be summarized by treatment group. Descriptive statistics will be presented for observed values and changes from baseline at each visit where parameters were scheduled to be collected per the clinical study protocol.

Where applicable, laboratory results will be classified as “low,” “normal,” or “high” with respect to the parameter-specific reference ranges (i.e., below the lower limit of the normal range, within the normal range, or above the upper limit of the normal range). Three-by-three contingency tables will be presented for each laboratory parameter to summarize the shift from the baseline category to the worst post-baseline measurement, defined as the value numerically farthest outside of the normal range across all post-baseline visits through the end of the study.

Summary results will include the count and percentage of subjects within each shift category and treatment group.

7.5.6 Vital Signs, Physical Findings, and Other Observations Related to Safety

7.5.6.1 Vital Signs

Vital sign parameter measurements will be summarized by treatment group. Descriptive statistics will be presented for results and change from baseline at each visit where parameters were scheduled to be collected.

7.5.6.2 Physical Examination

Results of the physical examination will be presented in subject data listings by subject, study visit, and body system.

7.5.6.3 Prior and Concomitant Medications

Medications will be coded using the World Health Organization (WHO) drug dictionary, enhanced (version B2 March 1, 2016). Medications entered on the eCRF will be mapped to Anatomic Therapeutic Chemical (ATC) drug class (level 4) and drug name.

Prior and concomitant medications will be summarized separately and the study phase of each medication will be determined programmatically based on medication start and end dates. A

prior medication is defined as any medication administered prior to the date of the first dose of study drug. A concomitant medication is defined as any medication administered on or after the date of the first dose of study drug. A medication may be defined as both prior and concomitant. If it cannot be determined whether a medication was received prior to the start of study drug dosing due to partial or missing medication start and/or end dates, it will be considered a prior medication. Likewise, if it cannot be determined whether a medication was received after the start of study drug dosing, it will be considered concomitant.

For the summary of both prior medications and concomitant medications, the number and percentage of subjects receiving any medication will be summarized by treatment group, as will the number and percentage receiving any medication by ATC drug class and generic drug name. Subjects reporting use of more than one medication at each level of summarization (any medication received, ATC class, and generic drug name) will be counted only once. ATC class terms will be displayed by descending order of incidence, as will generic drug names within each ATC class. The study phase during which each medication was received (e.g., prior, concomitant, or both) will be presented on the listing of prior and concomitant medications.

7.5.6.4 *Prior and Concomitant Therapies/Procedures*

Therapies/Procedures will be coded using MedDRA version 19.1. Therapies entered on the eCRF will be mapped to SOC.

The study phase of each therapy/procedure will be determined programmatically based on start and end dates. A prior therapy/procedure is defined as any therapy/procedure occurring prior to the date of the first dose of study drug. A concomitant therapy/procedure is defined as any therapy/procedure occurring on or after the date of the first dose of study drug. A therapy/procedure may be defined as both prior and concomitant. If it cannot be determined whether a therapy/procedure occurred prior to the start of study drug dosing due to partial or missing, it will be considered a prior therapy/procedure. Likewise, if it cannot be determined whether a therapy/procedure occurred after the start of study drug dosing, it will be considered concomitant. Therapies and procedures will be reported in a subject listing, and identified as prior or concomitant, and as a therapy or a procedure.

7.6 **Determination of Sample Size**

For the binary version of the primary endpoint, i.e., proportion of subjects achieving at least a 1-point improvement in HDSM-Ax from baseline to end of therapy, the true response rates will be assumed to be 75% for each BBI-4000 arm and 50% for vehicle control (based on prior data). With 100 evaluable subjects at a 1:1 ratio for each pairwise comparison between a BBI-4000 arm and the vehicle arm, i.e., 50 evaluable subjects per arm, the power is approximately 0.87 for observing a response rate difference in favor of BBI-4000 at a 1-sided $p < 0.10$ level.

For the continuous version of HDSM-Ax change from baseline to end of therapy, the true mean difference between each BBI-4000 arm and the vehicle arm will be assumed to be 0.18, with a common standard deviation of 0.36, i.e., an effect size (mean difference/standard deviation) of

0.50. With 100 evaluable subjects at a 1:1 ratio for each pairwise comparison between a BBI-4000 arm and the vehicle arm, the power is approximately 0.89 for observing a difference in favor of BBI-4000 at a 1-sided $p < 0.10$ level.

Assuming an approximate 10% non-evaluable rate for the mITT primary efficacy analyses, 220 randomized subjects are targeted for enrollment.

